2.3 Research Design

The following 2 groups of patients will participate in the proposed studies of Specific Aim #2: (1) SD patients, and (2) SD/VT patients. Because sodium oxybate has been shown to be effective in patients with movement disorders who self-report symptom improvement after alcohol intake, only ethanol-responsive patients will be recruited for the purposes of these studies. We estimate that 60% of ethanol-responsive patients per group, who participated in the studies in Specific Aim #1, will also participate in the studies in Specific Aim #2. Both ADSD and ABSD patients will be included and closely matched with ADSD/VT and ABSD/VT patients. Patients will be identified according to the screening and detailed examinations as described in Specific Aim #1. In this Specific Aim, we will (1) evaluate the central effects of sodium oxybate in SD and SD/VT patients to determine the relationship between improved clinical symptoms and modulated brain function, and (2) examine the extent of central effects from the combined use of sodium oxybate and botulinum toxin treatments as an alternative treatment schedule for patients with limited benefits.

2.3.1 Study #1: Mapping central effects of sodium oxybate treatment in patients with SD and SD/VT using fMRI during symptomatic speech production. Similar to the fMRI study under Specific Aim #1, we will use a sparse-

sampling event-related BOLD fMRI design during symptomatic voice and speech production on a 3.0 Tesla Philips MRI scanner. Each patient will participate in 2 fMRI sessions, before and after treatment with sodium oxybate. All recruited patients will have to be symptomatic; if they are treated with botulinum toxin injections, they may be included only if they are symptomatic at the end of their botulinum toxin treatment cycle. During each scanning session, the patient will be asked to perform short English sentences as well as repetitive and continuous vowel /i/, designed to elicit SD and VT symptoms. Four scanning sessions will be acquired with a total of 36 experimental trials and 24 baseline resting conditions. Structural MRI will be acquired for an anatomical reference.

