Study population and Sample size. To our knowledge the central effects of sodium oxybate has not been reported. Therefore, to estimate the number of patients to be included in this study, we reviewed our pilot fMRI study in SD and SD/VT patients. Compared to baseline, we found an average of 49% reduction of overly increased brain activation after treatment with sodium oxybate. Power analysis determined a sample size of 22 patients in each group to have 80% power at 0.025 to detect changes in brain activation when comparing before and after treatment conditions. We propose to recruit 25 ethanol-responsive SD and SD/VT subjects per group to account for the subjects' dropout possibilities and to increase statistical power.

2.3.2 Study #2: Evaluation of combined central effects of sodium oxybate and botulinum toxin treatments in patients with SD and SD/VT using fMRI during symptomatic speech production. In this study, we will use the same fMRI design as used in the Similar to *Studies 1.3.1* and *2.3.1* to examine the combined effects of sodium oxybate and botulinum toxin on brain activation changes due to the treatment.

We estimate that about 40% of all recruited patients (mostly with ADSD) will report some benefits from botulinum toxin injections. These patients will be enrolled in this study and will undergo the third scanning session after receiving their botulinum toxin treatment. They will be asked to take their individualized dose of sodium oxybate T.I.D. after the completion of the *Study 2.3.1* and until the end of this study. We predict that about 60% of SD (typically ABSD) and SD/VT patients recruited to the *Study 2.3.1* will report limited, if any, benefits from botulinum toxin treatment. These patients will, therefore, be replaced with newly recruited patients, whose symptoms do response to both alcohol intake and botulinum toxin treatment. Thus, at the time of this study, all patients will be treated with both sodium oxybate and botulinum toxin injections. The decision of whether sodium oxybate should be continued after the completion of all studies in this proposal will be made by the patient and his/her referring physician.

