a. **Human Subjects Involvement, Characteristics, and Design.** As described in the *Approach* section, we will recruit SD, SD/VT and healthy control subjects for participation in the proposed studies. Both ADSD and ABSD patients as well as ADSD/VT and ABSD/VT patients will be included and matched with each other in their age, gender and SD type (AD or AB). Clinically healthy subjects will be those who do not have present or past history of any neurological, psychiatric or laryngological problems. Controls will be carefully matched with SD and SD/VT populations by their age, gender, and ethnicity.

For all studies in Specific Aim #1, we propose to recruit the same 20 subjects per SD, SD/VT and control groups. Because the majority of VT patients report improvement of their voice symptoms after alcohol intake, we predict that at least 60% (12 patients) of recruited SD/VT group will also be ethanol-responsive. To assure homogeneity between patient populations, we will carefully match SD and SD/VT patients according to their report of alcohol effects, in addition to their age, gender and an SD type match. A total of 60 subjects will undergo 2-hour scanning session for the studies in Specific Aim #1.

For all studies in Specific Aim #2, we will recruit 25 ethanol-responsive SD and SD/VT patients. We estimate that 12 ethanol-responsive patients per group, who participated in the studies in Specific Aim #1, will also participate in the studies in Specific Aim #2. Thus, this will require us to recruit additional 13 SD and 13 SD/VT patients for the proposed studies in Specific Aim #2. A total of newly recruited patients will be 26. The patients will participate in the fMRI studies of this Specific Aim according to the following schedule:

- (1) Because the 12 patients/group, who already underwent neuroimaging studies in Specific Aim #1, will not need a pre-treatment baseline scanning session, they will only complete two 2-hour post-treatment scans with sodium oxybate and botulinum toxin + sodium oxybate, respectively;
- (2) the remaining 13 patients/group will complete three 2-hour scanning sessions, which will include one pre-treatment baseline scan and two post-treatment scans with sodium oxybate and botulinum toxin + sodium oxybate, respectively.

A total number of subjects recruited for studies under both Specific Aims will be 86.

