5. To avoid the possibility of confounding effects of drugs acting upon the central nervous system, all study participants will be questioned about *any* prescribed or over-the-counter medications as part of their initial intake screening (see **Appendix 1**). Those patients who receive medication(s) affecting the central nervous system (except sodium oxybate as part of the studies under Specific Aim #2) will be excluded from the study.
6. The patients will be asked whether they have undergone any head and neck surgeries, particularly any brain surgery and laryngeal surgeries, such as thyroplasty, laryngeal denervation, and selective laryngeal adductor denervation-reinnervation (see **Appendix 1**). Because both brain and laryngeal surgery may potentially lead to the brain structure and function re-organization, all patients with history of brain and/or laryngeal surgery will be excluded from the study.
7. Subjects who have tattoos, ferromagnetic objects in their bodies (e.g., implanted stimulators, surgical clips, prosthesis, artificial heart valve, etc.) that cannot be removed for the purpose of study participation.

Subjects accepted into the study will require up to four visits for patients and up to two visits for healthy controls, including one screening visit (intake questionnaire, self-screening questionnaire, voice and speech recording, nasolaryngoscopy, neurological exam) and one to three scanning session depending whether healthy control or patient. Time commitment for the screening visit may be up to 3 hours for patients and 1 hour for healthy volunteers; fMRI, MRI and DTI will be combined into the same scanning session of up to 2 hours. Scanning sessions will be scheduled according to the treatment schedule.

b. Sources of Material. Every effort will be made to respect and maintain the confidentiality of study participants according to the current legal requirements and as required by the Federal Privacy Act. The TBR Research Associate will be directly involved in the maintaining of subject databases, ensuring that strict standards of confidentiality are upheld at all times. Only the research team will have access to the research

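### The recruitment total of 86 and the scan schedule omit the replacement patients that Study 2.3.2 calls for (about 30 people on the plan's own 60% figure)

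*Combined protocol and SAP*

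**What the plan says.** Two parts of the combined protocol and SAP describe who takes part in Study 2.3.2, the combined sodium oxybate and botulinum toxin study.

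**Research plan, section 2.3.2.** About 40% of recruited patients are expected to report some benefit from botulinum toxin; these go on to the combined study. About 60% of the SD and SD/VT patients in Study 2.3.1 are expected to report little or none. Of the latter it says: "These patients will, therefore, be replaced with newly recruited patients, whose symptoms do response to both alcohol intake and botulinum toxin treatment". The section adopts the fMRI design and analysis of Study 2.3.1 and states that its power is the same.

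**Protection of Human Subjects, section 1a.** Aim 1 takes 20 subjects in each of three groups. Aim 2 takes 25 ethanol-responsive patients per group, of whom 12 per group come from Aim 1. On the other 13 per group: "A total of newly recruited patients will be 26". Overall: "A total number of subjects recruited for studies under both Specific Aims will be 86". The schedule has two lines:

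- The 12 per group from Aim 1 already have a baseline, so "they will only complete two 2-hour post-treatment scans with sodium oxybate and botulinum toxin + sodium oxybate, respectively".
- For the others, "the remaining 13 patients/group will complete three 2-hour scanning sessions, which will include one pre-treatment baseline scan and two post-treatment scans", the two being sodium oxybate alone and the combination.

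Neither the counts nor the schedule mentions replacements.

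**The concern.** The research plan recruits a further set of patients for Study 2.3.2, and the section that states how many people will be enrolled does not include them. The 26 new patients cannot double as the replacements: all of them are needed to bring Study 2.3.1 from 12 to 25 per group, and each already has a three-scan schedule.

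The schedule also conflicts on who is scanned under combined treatment. The human-subjects section sends all 25 per group to that scan; section 2.3.2 sends only those with some botulinum toxin benefit and replaces the others. This conflict remains even if the 60% estimate proves wrong.

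At stake are the stated number of people exposed to sodium oxybate for the study, the recruitment target in a disorder that the plan calls relatively rare, and the sample size of Study 2.3.2, whose claim of equal power depends on the replacements being recruited.

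**Working it through.** **Inputs**

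- Aim 1: 20 per group, three groups (Protection of Human Subjects, 1a).
- Aim 2: 25 per group, two groups; 12 per group carried over from Aim 1 (same section; 25 also in 2.3.1).
- Replaced share: about 60% of Study 2.3.1 patients (2.3.2).
- Powered sample size: 22 per group, 80% power at 0.025 (2.3.1).

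**Reproducing the plan's total**

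- Aim 1: 20 × 3 = 60.
- New Aim 2 patients: (25 − 12) × 2 = 26.
- Total: 60 + 26 = 86. This matches exactly, so 86 contains no replacements.

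**Adding the replacements**

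- Study 2.3.1 patients: 25 × 2 = 50.
- Replaced: 0.60 × 50 = 30. Kept: 50 − 30 = 20.
- One-for-one replacement: 86 + 30 = 116 in total (30/86 = 35% more); new Aim 2 recruits 26 + 30 = 56.
- Refilling only to 22 per group: 44 − 20 = 24 replacements; 86 + 24 = 110 in total; new Aim 2 recruits 26 + 24 = 50.

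**Scan sessions**

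- Implied by the human-subjects schedule: 60 + 24 × 2 + 26 × 3 = 60 + 48 + 78 = 186.
- Aim 1 plus Study 2.3.1 only: 60 + 24 × 1 + 26 × 2 = 60 + 24 + 52 = 136.
- Under section 2.3.2, add one combined scan for each of the 20 kept patients and k scans for each of 30 replacements: 136 + 20 + 30k.

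| Scans per replacement (k) | Total sessions |
|---|---|
| 1 (combined only) | 186 |
| 2 (pre-treatment and combined) | 216 |
| 3 (also sodium oxybate alone) | 246 |

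The documents do not give k. With k = 1 the total equals the one already implied.

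**If 86 is kept and nobody is replaced**

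- Study 2.3.2 would have 0.40 × 50 = 20 patients, about 10 per group if the split is even.
- The plan gives no SD for the change in activation, so the effect is back-solved. A paired t-test with n = 22, 80% power and two-sided 0.025 implies a mean change of 0.70 SD of the change.
- At that effect, 10 pairs give about 37% power. For comparison, 25 pairs give about 86%.

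**The case against.** The 40% and 60% figures are forecasts, and enrolment totals in a research plan are often approximate. No analysis or error rate changes if the replacements are in fact recruited as section 2.3.2 says, and most of the correction is wording. This stands, and it limits the seriousness of the point. It does not remove the conflict, because the total of 86 leaves no room for replacements at all and the schedule contradicts the replacement rule whatever the share.

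One might fill the gap from Aim 1 patients not used in Aim 2, (20 − 12) × 2 = 16 people. Section 2.3.2 says the replacements are newly recruited, and Aim 2 admits only ethanol-responsive patients. For the SD/VT group, "we predict that at least 60% (12 patients) of recruited SD/VT group will also be ethanol-responsive", and those 12 are already counted in Aim 2. Even if all 16 qualified, 30 − 16 = 14 people would still be missing.

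Three stronger readings are tempting and are not supported:

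- **That the plan exceeds its own scan schedule.** With one combined scan per replacement the total is 186, as the schedule implies. What the documents support is that replacements have no schedule line.
- **That the power statement for Study 2.3.2 is false.** As to sample size, it can hold if replacements restore 22 to 25 fully paired patients per group. It fails only if 86 is kept without replacement, on the back-solved effect.
- **That all the uncounted people would be given both treatments because of the study.** They are chosen because they already respond to botulinum toxin, and the procedures list allows injection by the patient's own laryngologist. The clearly study-driven exposure is sodium oxybate.

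**Conclusion.** The point holds as an internal contradiction that is wrong as written and should be fixed. The recruitment total of 86 and the new-recruit count of 26 omit the Study 2.3.2 replacements, and the schedule sends to the combined scan patients whom section 2.3.2 replaces.

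On the plan's own 60%, one-for-one replacement gives about 30 more people, 116 in total and 56 new Aim 2 recruits; refilling to 22 per group gives 24 more and 110 in total. These figures assume that the 60% applies to all 50 Study 2.3.1 patients and that replacements come from outside Aim 1, as the text says. A wider range would need replaced shares that the plan does not give, so none is offered.

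The 37% power figure applies only if there is no replacement; it rests on an even split between groups and on the back-solved effect. Aim 1 and Study 2.3.1 are unaffected.

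**What to change.** Reconcile sections 2.3.2 and 1a of Protection of Human Subjects in one of two ways.

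**If the replacement rule stands:**

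1. Restate the overall total and the number of new Aim 2 recruits, giving the assumed replaced share and whether groups are refilled to 25 or to 22 (116 and 56, or 110 and 50, at 60%).
2. Correct the schedule so that patients who are replaced are not listed for the combined scan.
3. Add a schedule line for replacements that includes their own pre-treatment scan as well as the combined scan. Study 2.3.1, whose design Study 2.3.2 adopts, is within-patient: "Each patient will participate in 2 fMRI sessions, before and after treatment with sodium oxybate". Without a pre-treatment scan, replacements could not contribute to the comparison of pre-treatment with combined treatment.

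**If 86 is the intended total:** remove the replacement sentence, state that Study 2.3.2 has about 20 patients in all (about 10 per group), and replace the statement of equal power with a calculation for that number.

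**Cost.** The stated total becomes less favourable. Pre-treatment scans for 30 replacements add 30 two-hour sessions (60 scanner hours; 216 sessions against 186). Two scans per replacement stay within the visit plan, which allows "one to three scanning session depending whether healthy control or patient". Screening takes up to 3 hours per patient, so up to 30 × 3 = 90 hours for those enrolled, plus any screen failures against the requirement of response to both alcohol and botulinum toxin. The recruitment itself is already implied by section 2.3.2.

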Our long-term goal is to determine the pathophysiology of SD and related disorders, such as VT, and develop new diagnostic and treatment options for these patients. The objective of this application is to identify brain abnormalities in SD and SD/VT patients as the basis for characterization of central mechanisms underlying symptom improvement following the use of sodium oxybate. Our central hypothesis is that, compared to SD patients, SD/VT patients will have additional brain abnormalities within the sensorimotor brain circuits controlling voice production, which are being modulated to a greater extent with sodium oxybate treatment. We further postulate that the clinical efficacy of sodium oxybate treatment will correlate with its central modulatory effects. The rationale for the proposed research is that identification of distinct brain mechanisms underlying SD and SD/VT clinical manifestations would provide the necessary insights into the pathophysiology of these disorders, while understanding the neural correlates of sodium oxybate action would allow establishment of a scientific rationale for the use of a novel treatment in these disorders.

We propose the following two specific aims:

1. Determine disorder-specific brain abnormalities in SD and SD/VT patients. Based on our preliminary data, our *working hypothesis* is that distinct brain abnormalities will be present in SD and SD/VT patients, who also share common abnormalities within the sensorimotor brain networks controlling voice production.

2. Characterize the central effects of sodium oxybate treatment in ethanol-responsive SD and SD/VT patients. Based on our preliminary data, our *working hypothesis* is that the greater beneficial effects of sodium oxybate treatment in SD/VT patients compared to SD patients are due to a greater extent of modulation of their abnormal brain activation.

At the completion of these studies, it is our expectation that we will have (i) identified characteristic profiles of brain abnormalities in SD and SD/VT patients, (ii) determined the extent of their modulation with a novel treatment, sodium oxybate, both of which will be critical for (iii) establishment of neural markers and a new therapeutic option for patients who do not benefit from botulinum toxin treatment alone. These results are expected to have an important positive impact, because they will fundamentally advance our knowledge of the pathophysiology of SD and VT as well as allow for improved treatment.

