Because more than 50% of patients experience breathiness with mean duration of 10.3 days and 14% of patients develop dysphagia to liquids with mean duration of 2 days as most common side effects following botulinum toxin injections (Novakovic et al., 2011), we will acquire the fMRI data at least 14 days after the botulinum toxin treatment.

We will use the same *fMRI design* as in the *Studies 1.3.1* and *2.3.1*. *Data analysis* will follow the same pipeline as described in *Study 2.3.1*. The power for this study is the same as in *Study 2.3.1*.

2.4 Expected Outcomes. Upon the successful completion of the studies in Specific Aim #2, we expect to have determined the brain mechanisms of action of a novel pharmacological agent, sodium oxybate, as a potentially alternative treatment for symptom management in SD and SD/VT patients. Furthermore, we expect to identify the extent of central effects from the combined use of sodium oxybate and botulinum toxin. This treatment strategy may be useful in prolongation of the effects of botulinum toxin injections in those patients who receive limited benefits, mainly due to presence of the VT component. Collectively, we expect that outcome of the proposed studies will establish a strong scientific basis for the use of newly developed treatment strategies in SD and SD/VT patients.

2.5 Potential Problems and Alternative Strategies. Similar to the studies under Specific Aim #1, a potential problem may arise from an insufficient availability of patients who must be symptomatic and ethanol-responsive. However, such a problem seems unlikely for reasons described under subsection 1.5.

A different strategy for the evaluation of central effects of sodium oxybate might be the initial conduct of large-scale clinical trials using this drug in SD and VT and then exploration of its central mechanism of action in these patients. We, however, decided against this strategy because the establishment of a scientific basis for the use of sodium oxybate in SD and VT patients is of a more importance than the empirical test of yet another medication in these patients. Furthermore, the conduct of a large-scale clinical trial from the statistical point of view may be difficult as the recruitment of large numbers of eligible patients with these rare disorders may present a significant challenge.

Timetable

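### Study 2.3.2 enrols patients with botulinum toxin benefit, so its conclusion for limited-benefit patients is unsupported, and the total of 86 leaves out the replacements

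*Combined protocol and SAP*

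**What the plan says.** Four places in the combined protocol and SAP bear on who Study 2.3.2 is about.

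- **2.3 Research Design (Specific Aim #2), objective (2).** The combined use of the two treatments is to be examined "as an alternative treatment schedule for patients with limited benefits".
- **2.3.2 Study #2.** The study's own aim carries no population limit: "to examine the combined effects of sodium oxybate and botulinum toxin on brain activation changes due to the treatment". Enrolment does. About 40% of all recruited patients, mostly with adductor SD (ADSD), are expected to report some toxin benefit, and these are enrolled. About 60% of the SD (typically abductor, ABSD) and SD/VT patients from Study 2.3.1 "will report limited, if any, benefits from botulinum toxin treatment". Of the latter the plan says: "These patients will, therefore, be replaced with newly recruited patients, whose symptoms do response to both alcohol intake and botulinum toxin treatment".
- **2.4 Expected Outcomes.** The combination is put forward, with a hedge, as "useful in prolongation of the effects of botulinum toxin injections in those patients who receive limited benefits, mainly due to presence of the VT component".
- **Protection of Human Subjects, 1a.** In each group, 12 patients carried over from Aim 1 and 13 new ones all complete a combined-treatment scan. New recruits for Aim 2 number 26, and the total for both aims is 86. Replacement is not mentioned.

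**The concern.** The objective and the expected outcome name patients with limited benefit. The enrolment rule uses nearly the same words for the patients it takes out. Nothing elsewhere brings them back into 2.3.2, for example as a subgroup. The rule falls mainly on ABSD and SD/VT patients, and SD/VT is the group to which 2.4 ties its conclusion.

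At stake is what the third scan can be said to show. A combined effect seen in patients who already gain from toxin does not establish that adding oxybate changes brain activation in patients for whom toxin does little. Analysis cannot recover this afterwards if those patients were not scanned. The recruitment total is also affected, because replacements are extra people and the stated total has no room for them.

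**Working it through.** **1. Populations side by side.**

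| Place | Who the combined study concerns |
|---|---|
| 2.3, objective (2) | patients with limited benefit |
| 2.3.2, aim sentence | no restriction |
| 2.3.2, enrolment | patients with some toxin benefit; those with little or none replaced by responders to alcohol and toxin |
| 2.4 | patients with limited benefit, mainly because of VT |
| Human Subjects 1a | the same 25 per group, no replacement |

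Rows 1 and 4 agree with each other. Row 3 takes out the patients with little or no toxin benefit. Row 5 would leave them in. Rows 3 and 5 cannot both be followed.

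**2. The plan's own head count.** Inputs: 20 subjects in each of 3 Aim 1 groups; 25 per group in Aim 2; 12 per group carried over from Aim 1 (60% of 20).

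- Aim 1: 3 × 20 = 60
- New for Aim 2: 2 × (25 − 12) = 26
- Total: 60 + 26 = 86

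This reproduces the stated 86 exactly, with no replacement patients in it.

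**3. Head count under the 2.3.2 rule.** Study 2.3.1 has 2 × 25 = 50 patients.

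- Retained: 0.40 × 50 = 20, pooled over both groups
- Replaced: 0.60 × 50 = 30, pooled
- Total recruited: 86 + 30 = 116

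The 60% is the plan's prediction. Varying it as an assumption:

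| Share replaced | Replacements (of 50) | Total recruited |
|---|---|---|
| 50% | 25 | 111 |
| 60% | 30 | 116 |
| 70% | 35 | 121 |

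**4. Whether replacements could simply be left out.** Section 2.3.2 takes its power from Study 2.3.1, which asks for 22 per group, or 44 in all. The 20 retained patients fall well short. If the toxin-benefit restriction stands, the replacements are needed and the total of 86 cannot be kept.

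**5. What the planned analysis could separate.** Section 2.3.2 follows the 2.3.1 pipeline: a two-way ANOVA with subject and task, then a conjunction analysis across sessions within the patient group. Degree of toxin benefit is not a factor, and the text gives no cut-off between some and limited benefit.

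**The case against.** The best defence is that the contradiction is not total. Section 2.4 speaks of prolonging a toxin effect, and an effect must exist before it can be prolonged. On that reading, limited benefit means a partial response with residual tremor. The Specific Aims and the pilot data in 2.2.2 fit it: the former speaks of symptoms not fully managed by toxin, and the latter reports a longer toxin cycle in patients using both treatments. Patients with some benefit, whom 2.3.2 enrols, can include such partial responders. This stands. A reader might infer that the study cannot address its objective at all, or that no limited-benefit patient would remain. The documents do not support that, because some benefit is nowhere equated with full response. What is missing is a definition of partial response and any analysis by it.

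Other points also stand in part:

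- Objective (2) does not say limited benefit *from toxin*. That is an inference, though 2.3.2 and 2.4 make it the natural one.
- The aim sentence inside 2.3.2 can be met as written, and 2.4 is hedged. The hedge covers usefulness, however, and leaves the named population unchanged.
- Patients with little toxin benefit stay in Study 2.3.1 and are studied on oxybate. The Specific Aims expectation of "a new therapeutic option for patients who do not benefit from botulinum toxin treatment alone" rests on oxybate and is not defeated by the replacement rule.
- If the Human Subjects schedule were followed, limited-benefit patients would be scanned. That makes it a further conflict to settle and does not resolve the one above.

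**Conclusion.** The point holds in this form. As 2.3.2 is written, the study can describe combined effects on brain activation in patients with at least some toxin benefit. It does not support a conclusion for patients with limited or no benefit, because partial responders, if present, are neither identified nor analysed separately. The recruitment total is understated by about 30 (about 116 against 86) if replacement stands. This rests on the plan's 60% prediction, on applying it to all 50 Study 2.3.1 patients, and on each replaced patient giving way to one new recruit.

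Two further inferences should not be drawn. A reader might turn the 60% into 15 of 25 replaced in each group. The plan gives no split by group, and its own remarks point to unequal shares: about 80% ADSD expected (1.3), 90% of ADSD patients benefiting, and much less benefit in SD/VT (2.1). A reader might also infer that selecting toxin responders shrinks the SD versus SD/VT contrast. The documents give no data on this, and the analysis inherited from 2.3.1 specifies no between-group factor.

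**What to change.** - Restate objective (2) in 2.3 and the expected outcome in 2.4 as applying to ethanol-responsive patients who report toxin benefit, and drop the inference to patients with limited or no toxin benefit.
- Reconcile 2.3, 2.3.2, 2.4 and Protection of Human Subjects 1a on who has the combined-treatment scan.
- If replacement stands, correct the total of 86 and the figure of 26 new Aim 2 recruits. On the 60% estimate the total becomes about 116 and the new recruits 26 + 30 = 56.

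The cost is a narrower claim and a larger stated recruitment total. The rewording needs no scans beyond those that 2.3.2 already implies. Which patients receive toxin remains a clinical decision, and nothing here bears on it.
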